Appendix 1: Administrative procedures

Regulatory and ethical compliance

This clinical study was designed and shall be implemented and reported in accordance with the ICH Harmonized Tripartite Guidelines for Good Clinical Practice, with applicable local regulations (including European Directive 2001/83/EC and US Code of Federal Regulations Title 21), and with the ethical principles laid down in the Declaration of Helsinki.

Responsibilities of the investigator and IRB/IEC/REB

The protocol and the proposed informed consent form must be reviewed and approved by a properly constituted Institutional Review Board/Independent Ethics Committee/Research Ethics Board (IRB/IEC/REB) before study start. A signed and dated statement that the protocol and informed consent have been approved by the IRB/IEC/REB must be given to Novartis before study initiation. Prior to study start, the investigator is required to sign a protocol signature page confirming his/her agreement to conduct the study in accordance with these documents and all of the instructions and procedures found in this protocol and to give access to all relevant data and records to Novartis monitors, auditors, Novartis Clinical Quality Assurance representatives, designated agents of Novartis, and regulatory authorities as required.

Informed consent

Eligible patients may only be included in the study after providing written (witnessed, where required by law or regulation), IRB/IEC/REB-approved informed consent, or, if incapable of doing so, after such consent has been provided by a legally acceptable representative of the patient. Informed consent must be obtained before conducting any study-specific procedures (i.e., all of the procedures described in the protocol). The process of obtaining informed consent should be documented in the patient source documents.

The informed consent form that complies with regulatory requirements and is considered appropriate for this study is provided separately. Any changes to the consent form suggested by the investigator must be agreed to by Novartis before submission to the IRB / IEC / REB, and a copy of the approved version must be provided to the Novartis monitor after IRB / IEC / REB approval.

Amendments to the protocol

Any change or addition to the protocol can only be made in a written protocol amendment that must be approved by Novartis, Health Authorities where required, and the IRB / IEC / REB. Only amendments that are required for patient safety may be implemented prior to IRB / IEC / REB approval. Notwithstanding the need for approval of formal protocol amendments, the investigator is expected to take any

immediate action required for the safety of any patient included in this study, even if this action represents a deviation from the protocol. In such cases, Novartis should be notified of this action and the IRB / IEC / REB at the study site should be informed within 10 working days.

Discontinuation of the study

Novartis reserves the right to discontinue this study under the conditions specified in the clinical trial agreement.

Study drug supply and resupply, storage, and tracking

Study drugs must be received by a designated person at the study site, handled and stored safely and properly, and kept in a secured location to which only the investigator and designated assistants have access. Upon receipt, the study medication should be stored according to the instructions specified on the drug labels. Clinical supplies are to be dispensed only in accordance with the protocol.

Medication labels will be in the local language and comply with the legal requirements. They will include storage conditions for the drug and the randomization number but no information about the patient.

The investigator must maintain an accurate record of the shipment and dispensing of study drug in a drug accountability ledger. Drug accountability will be noted by the field monitor during site visits and at the completion of the trial. Patients will be asked to return all unused study drug and packaging at the end of the study or at the time of study drug discontinuation.

At the conclusion of the study, and, as appropriate during the course of the study, the investigator will return all used and unused study drug, packaging, drug labels, and a copy of the completed drug accountability ledger to the Novartis monitor or to the Novartis address provided in the investigator folder at each site.

Appendix 2: Clinically notable laboratory values and vital signs

Notable criteria		
Laboratory variable	Standard units	SI units
Liver function and related variables		
SGOT (AST)	$\geq 3 \times$ ULN	$\geq 3 \times$ ULN
SGPT (ALT)	$\geq 3 \times$ ULN	$\geq 3 \times$ ULN
GGT	$\geq 3 \times$ ULN	$\geq 3 \times$ ULN
Bilirubin	≥ 2.0 mg/dL	≥ 34.2 μ mol/L
Alkaline phosphatase	$\geq 3 \times$ ULN	$\geq 3 \times$ ULN
Albumin	None	None
Total protein	None	None
Renal function, metabolic and electrolyte variables		
Urea	None	None
Creatinine	>30% above baseline	>30% above baseline
Uric acid	M ≥ 12 mg/dL F ≥ 9 mg/dL	M ≥ 714 μ mol/L F ≥ 535 μ mol/L
Glucose	<45 mg/dL >250 mg/dL	<2.5 mmol/L >13.9 mmol/L
Cholesterol	≥ 350 mg/dL	≥ 9.1 mmol/L
Triglycerides	≥ 750 mg/dL	≥ 8.5 mmol/L
CPK (MB)	None	None
Sodium	None	None
Chloride	None	None
Potassium	≤ 3.0 mEq/L ≥ 6.0 mEq/L	≤ 3 mmol/L ≥ 6 mmol/L
Magnesium	<0.97 mg/dL >3.65 mg/dL	<0.4 mmol/L >1.5 mmol/L
Calcium	≤ 6 mg/dL ≥ 13 mg/dL	≤ 1.5 mmol/L ≥ 3.2 mmol/L
Phosphate	None	None
Amylase	$\geq 2 \times$ ULN	$\geq 2 \times$ ULN
Testosterone*	None	None
LH	None	None
FSH	None	None
Lipase	$\geq 2 \times$ ULN	$\geq 2 \times$ ULN

*male patients

Notable criteria		
Laboratory variable	Standard units	SI units
Hematology variables		
Hemoglobin	<7 g/dL	<4.39 mmol/L
Platelets (thrombocytes)	<50 k/mm ³ ≥700 k/mm ³	<50 × 10 ⁹ /L ≥700 × 10 ⁹ /L
Leukocytes (WBCs)	≤2.0 k/mm ³ ≥16 k/mm ³	≤2.0 × 10 ⁹ /L ≥16 × 10 ⁹ /L
Hematology variables: differential		
Granulocytes (poly, neutrophils)	≤1,000/mm ³	≤1 × 10 ⁹ /L
Eosinophils	≥12%	≥12%
Lymphocytes	≤1,000/mm ³	≤1 × 10 ⁹ /L
Urinalysis		
Albumin (mg/dL)	None	None
Glucose (mg/dL)	None	None
Erythrocytes	None	None
Protein/creatinine	<200 mg/g	<22.7 mg/mmol

Harmonized notable vital signs (and weight)

Vital sign variables	Notable criteria
Pulse (beats/min.)	None
Systolic BP (mm/Hg)	Either an increase of ≥30 that results in ≥180 or >200 (mm/Hg) or a decrease of ≥30 that results in ≤90 or <75 (mm/Hg)
Diastolic BP (mm/Hg)	Either an increase of ≥20 that results in ≥105 or >115 (mm/Hg) or a decrease of ≥20 that results in ≤50 or <40 (mm/Hg)
Temperature (°C)	None
Weight (kg)	None

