Screening Visit - Visit 1 (Month 3 post Tx)

This visit may be performed within a time window of \pm 2 weeks.

1. Patient signs informed consent.
2. Patient's eligibility for the study according to in- and exclusion criteria will be checked.
3. Demographic data will be recorded (sex, age, ethnic origin).
4. Relevant medical history as well as renal history (**especially information on dialysis**) will be obtained and recorded.
5. Transplantation information will be recorded (donor and recipient information, including viral serology; initiated immunosuppressive regimen, including induction therapy).
6. A complete physical examination will be performed.
7. Vital signs will be measured.
8. A 12-lead ECG will be written.
9. Venous blood will be drawn for measurement of hematology and biochemistry.
10. Viral serology of CMV (including pp65 Ag), Hepatitis B (HbsAg), Hepatitis C, and HIV will be recorded. Results from \leq 6 months prior Screening visit will be acceptable.
11. Venous blood will be drawn for measurement of the C0-h levels of Cyclosporin A or Tacrolimus and Everolimus.
12. Venous blood will be drawn for frozen storage until end of trial (2 EDTA-tubes, **2-5 mL**); only as a backup to repeat laboratory measurements if necessary).
13. In woman of childbearing potential a pregnancy test will be performed (β -HCG).
14. Urinalysis for proteinuria will be performed (spot urine sample for protein/creatinine ratio may be used).
15. Prior and concomitant medications / significant non-drug therapies will be recorded.
16. Immunosuppressive medication taken at M3 post Tx and any dose adjustments that were performed within the five days preceding the Screening visit will be recorded.

17. Information on rejection episodes and MACE that occurred since transplantation will be recorded.

Baseline Visit - Visit 2 (Month 6 post Tx)

This visit may be performed within a time window of \pm 1 week.

1. Patient's eligibility for the study according to in- and exclusion criteria will be checked
2. The patient will be randomized to one of the two treatment arms.
3. A complete physical examination will be performed.
4. Vital signs will be measured.
5. An endomyocardial biopsy will be performed.
6. A 12-lead ECG will be written.
7. Venous blood will be drawn for measurement of hematology and biochemistry.
8. Venous blood will be drawn for measurement of viral serology (CMV status including pp65 Ag).

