Abnormalities according notable criteria (see [Appendix 2](#)) will be identified. The proportions of patients with clinically notable abnormalities according to the notable criteria will be summarized. Shift tables describing changes from status prior transplantation (Month 0) and Baseline based on the expanded normal limits will be

presented for treatment endpoints (study Month 6 and 18) and worst observations during the different study periods (up to Month 6 as well as between Month 6 and Month 18). The worst observation is defined as the highest or lowest measure during the different observations periods whereby high or low are chosen according to the direction of abnormality (e.g. the highest will be chosen for serum creatinine, the lowest for leukocytes). Further, descriptive statistics of change from baseline of all laboratory variables will be presented by visit. A by-patient listing of all laboratory data (with clinically notable abnormalities being flagged) will be generated. Only assessments obtained up to 2 days after the discontinuation of study medication will be considered “on-treatment” and analyzed with relationship to Everolimus.

Vital signs

Vital signs variables include measurements of oral body temperature, systolic and diastolic blood pressures, pulse and body weight. Vital signs will be examined for abnormal values and change from Baseline according to pre-specified clinically notable criteria (see [Appendix 2](#)). Appropriate incidence rates of clinically notable abnormalities for between-group differences will be provided. Further, descriptive statistics of change from baseline of all vital signs variables will be presented by visit. A by-patient listing of all vital signs (with clinically notable abnormalities being flagged) will be generated. Shift tables describing changes from baseline based on clinically notable criteria will be presented for treatment endpoint (Month 18) and worst on-treatment observations. Only assessments obtained up to 2 days after the discontinuation of study medication will be considered “on-treatment”.

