### **2.7.3 Laboratory data**

Abnormalities according notable criteria (see [Appendix 2 of study protocol](#)) were identified. The proportions of patients with clinically notable abnormalities according to the notable criteria were summarized. Shift tables describing changes from status prior transplantation (Month 0) and Baseline based on the expanded normal limits were presented for treatment endpoints (study Month 6 and 18) and worst observations during the different study periods (up to Month 6 as well as between Month 6 and Month 18). The worst observation was defined as the highest or lowest measure during the different observations periods whereby

high or low were chosen according to the direction of abnormality (e.g. the highest will be chosen for serum creatinine, the lowest for leukocytes). Further, descriptive statistics of change from baseline of all laboratory variables were presented by visit. A by-patient listing of all laboratory data (with clinically notable abnormalities being flagged) was generated. Only assessments obtained up to 2 days after the discontinuation of study medication were considered “on-treatment” and analyzed with relationship to Everolimus.

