### **5.2.3.3 Other imputations**

## **5.3 AEs coding/grading**

## **5.4 Laboratory parameters derivations**

Clinically notable laboratory values and vital signs are defined in chapter 12, Appendix 2 of the study protocol.

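### The notable-value criterion for urine protein/creatinine in Protocol Appendix 2 points the wrong way, and the SAP adopts it uncorrected

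*Protocol*

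**What the plan says.** Protocol Appendix 2, headed "Appendix 2: Clinically notable laboratory values and vital signs", lists for each laboratory variable the values that count as notable. The last row of its urinalysis block is protein/creatinine. The entry is below 200 mg/g in the standard-units column and below 22.7 mg/mmol in the SI column. No upper limit is given. The urine albumin, glucose and erythrocyte rows read None.

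The purpose of the test is stated in the visit lists of Protocol section 7, for example at Screening: "Urinalysis for proteinuria will be performed (spot urine sample for protein/creatinine ratio may be used". Table 7-1 schedules it at Months 3, 6, 9 and 18.

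The criteria feed the analysis in three places:

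- Protocol 10.6.2: "The proportions of patients with clinically notable abnormalities according to the notable criteria will be summarized".
- SAP 2.7.3: "The proportions of patients with clinically notable abnormalities according to the notable criteria were summarized", and "A by-patient listing of all laboratory data (with clinically notable abnormalities being flagged) was generated".
- SAP 5.4: "Clinically notable laboratory values and vital signs are defined in chapter 12, Appendix 2 of the study protocol".

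SAP section 4, which lists departures from the protocol analyses, does not mention this row.

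**The concern.** A test ordered to find proteinuria has its abnormality at the high end. The printed limit puts it at the low end. A reader of the safety tables would take the count of notable protein/creatinine values as a count of patients with proteinuria, whereas as specified it counts patients without it. The same reversal would apply to the flags in the by-patient listing. Because the table is presented by treatment group, an excess of proteinuria in one arm would appear as fewer notable values in that arm. No other notable criterion would catch the problem, since urine albumin has none.

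**Working it through.** **1. Is the cut-off itself coherent?** The plan gives it as 200 mg/g and 22.7 mg/mmol. The conversion is mg/mmol = (mg/g) × M / 1000, where M is the molar mass of creatinine in g/mol. M is not in the documents, so I assume 113.0 to 113.6.

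- M = 113.0: 200 × 113.0 / 1000 = 22.60
- M = 113.12: 200 × 113.12 / 1000 = 22.62
- M = 113.6: 200 × 113.6 / 1000 = 22.72

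The stated 22.7 is reproduced to within 0.4% (0.10 / 22.7 at the lower end). The number is sound in both columns; only the direction is in question.

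**2. Is the sign an extraction fault?** Both unit columns carry the same less-than sign. Elsewhere the same table prints upper limits correctly: creatinine is notable at ">30% above baseline", and glucose has both a lower limit (45 mg/dL) and an upper limit (250 mg/dL). If an upper limit for the ratio had been lost, the printed lower limit would still flag patients without proteinuria.

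**3. Apply the rule to example ratios (mg/g).**

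| Ratio | Notable as printed (below 200) | Notable if reversed (above 200) |
|---|---|---|
| 50 | yes | no |
| 100 | yes | no |
| 199 | yes | no |
| 200 | no | no |
| 300 | no | yes |
| 1000 | no | yes |
| 3500 | no | yes |

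Apart from a value exactly at the cut-off, every flag swaps.

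**4. Effect on the table.** Take one visit, and patients with a recorded ratio. Let q₁ and q₂ be the shares below 200 mg/g in the two arms. The printed rule reports q₁ and q₂; the reversed rule reports about 1 − q₁ and 1 − q₂. The differences are related by

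(1 − q₁) − (1 − q₂) = −(q₁ − q₂),

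so the sign changes and the size does not. The documents give no values of q. As an illustration only, assume a range of 50% to 90% and put the arms at its ends: with q₁ = 50% and q₂ = 90%, the printed rule shows 50% against 90% (difference −40 points), and the reversed rule shows 50% against 10% (difference +40 points).

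**5. Limit of step 4.** The relation is exact only for one measurement per patient. With up to four scheduled visits, a patient at 100 mg/g on one visit and 300 mg/g on another is notable under either rule if any value counts. The two patient-level proportions then no longer add up to 100%.

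**6. Which outputs use Appendix 2?** The notable-value proportions and the listing flags do. In SAP 2.7.3 the laboratory shift tables rest on expanded normal limits instead, and the change-from-baseline statistics by visit use no limit.

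**The case against.** The best case for leaving this alone is that it is probably a slip in one row of a descriptive safety table, with a small reach. Several parts of that case stand.

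- The ratio is optional at each urinalysis, and the laboratory list in Protocol 7.6 names only urine protein. The number of patients with a recorded ratio is unknown and may be small.
- The data would not disappear. SAP 2.7.3 also lists every laboratory value by patient and summarises changes by visit, and Protocol 7.6 makes a clinically significant laboratory abnormality an adverse event. A patient at 3,000 mg/g would lack a flag but would still be listed.
- The intended entry is not documented. The row may be a reference range in the wrong column, with a different notable limit, or none, in mind.

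A reader might also infer more than the documents support. One inference is that the worst-value shift tables are inverted too. They are not built on Appendix 2; only the vital-sign shift tables use notable criteria (SAP 2.7.4.2). Another is that the program would pick each patient's lowest ratio as the worst. SAP 2.7.3 says that "high or low were chosen according to the direction of abnormality", but it does not tie that direction to Appendix 2, so for this variable the direction is unstated rather than reversed. A third is that the trial's main renal result is compromised. Protocol 7.7 does call renal safety and tolerability the main objective, but the renal variables it names are GFR and serum creatinine.

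None of this makes the printed criterion right. The proportion and the flags are planned outputs, and the relative frequency of abnormal laboratory parameters is among the key safety variables in SAP 2.7.1.

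**Conclusion.** Wrong as written. Under the printed rule, and among patients with a recorded ratio, the notable-value proportion and listing flags would mark those without proteinuria and never mark a measurement that shows it. At a single visit the difference between arms in this proportion would keep its size and take the opposite sign; for a count over several visits the inversion is only approximate.

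This rests on two assumptions: that the criterion is programmed as printed, which the documents do not show, and that a high ratio is the abnormality sought, which follows from the stated purpose of the test. The effect is confined to one row of a descriptive safety output. The laboratory shift tables, the change-from-baseline summaries, the primary GFR analysis, alpha and power are not affected by it.

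**What to change.** 1. Ask the sponsor to confirm the limit intended for urine protein/creatinine.
2. Add a line to SAP 5.4 that overrides the Appendix 2 row, so that ratios above the sponsor's own cut-off of 200 mg/g are notable. Keep 22.7 mg/mmol as stated; the rounding in the conversion gives no reason to change it.
3. Record the override in SAP section 4, so that the protocol appendix and the SAP do not stand in unexplained conflict.
4. State in SAP 2.7.3 that the worst protein/creatinine value is the highest.
5. Check the program for the notable-value table and the listing flags before database lock. The SAP's document history places this version before lock.

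The cost is a few SAP lines and one programming check. No new data are needed, and no other analysis changes.

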Appendix 3: Possible Cyclosporin A drug interactions

All of the individual drugs cited below are well substantiated to interact with Cyclosporin A. In addition, concomitant non-steroidal anti-inflammatory drugs, particularly in the setting of dehydration, may potentiate renal dysfunction.

A) Drugs that may potentiate renal dysfunction

Antibiotics	Antifungals	Gastrointestinal agents
Gentamicin	Amphotericin B	Cimetidine
Tobramycin	Ketoconazole	Ranitidine
Vancomycin		
Trimethoprim with-sulfamethoxazole		
Antineoplastics	Anti-inflammatory drugs	Immunosuppressives
Melphalan	Azapropazon Diclofenac Naproxen Sulindac	Tacrolimus

B) Drugs that alter Cyclosporin A concentrations

Cyclosporin A is extensively metabolized. Cyclosporin A concentrations may be influenced by drugs that affect microsomal enzymes, particularly cytochrome P-450 III-A. Substances that inhibit this enzyme could decrease metabolism and increase Cyclosporin A concentrations. Substances that are inducers of cytochrome P-450 activity could increase metabolism and decrease Cyclosporin A concentrations. Monitoring of circulating Cyclosporin A concentrations and appropriate **Cyclosporin A** dosage adjustments are essential when these drugs are used concomitantly.

Drugs that increase Cyclosporin A concentrations

Calcium channel blockers	Antifungals	Antibiotics
Diltiazem	Ketoconazole	Clarithromycin
Nicardipine	Fluconazole	Erythromycin
Verapamil	Itraconazole	
Glucocorticoids	Other drugs	
	Bromocriptine	
	Danazol	

Grapefruit and grapefruit juice affect Cyclosporin A metabolism, increasing blood concentrations of Cyclosporin A, thus should be avoided. Methylprednisolone, Metoclopramide, Allopurinol may have a small influence on Cyclosporin A metabolism, by slightly increasing blood concentrations of CsA. Thus, if patients are on methylprednisolone, metoclopramide, or allopurinol, the dose should be kept stable throughout the trial.

Drugs that decrease Cyclosporin A concentrations

Antibiotics	Anticonvulsants	Other drugs
Nafcillin Rifampin	Phenobarbital Phenytoin	Octreotide

Rifabutin is known to increase the metabolism of other drugs metabolized by the cytochrome P-450 system. The interaction between rifabutin and Cyclosporin A has not been studied. Care should be exercised when these two drugs are administered concomitantly. Troglitazone, Carbamazepine and Ticlopidine may also decrease CsA concentrations, but to a lesser extent. Thus, if patients are on stable therapy with these drugs, the dose should be kept stable throughout the trial, and patients should be closely monitored throughout the study.

Other drug interactions

Reduced clearance of prednisolone, digoxin and lovastatin and simvastatin has been observed when these drugs are administered with Cyclosporin A. In addition, a decrease in the apparent volume of distribution of digoxin has been reported after Cyclosporin A administration. Severe digitalis toxicity has been seen within days of starting Cyclosporin A in several patients taking digoxin. Cyclosporin A should not be used with potassium-sparing diuretics because hyperkalemia can occur.

During treatment with Cyclosporin A, vaccination may be less effective. The use of live vaccines should be avoided. Myositis has occurred with concomitant lovastatin and simvastatin, frequent gingival hyperplasia with nifedipine, and convulsions with high dose methylprednisolone.

Population screen for co-medications influencing Everolimus

Patients concomitantly receiving erythromycin antibiotics (erythromycin or azithromycin) had an average 20% lower Everolimus CL/F than those not receiving these co-medications. A single patient receiving itraconazole had a 3-fold lower Everolimus CL/F compared with the population average. These observations indicate that potent inhibitors of CYP3A can decrease the clearance of Everolimus and increase its blood levels.

Additional drugs or drug classes explored in the population model for which no influence on Everolimus CL/F was detected were: atorvastatin (n=74 patients), pravastatin (n=41), simvastatin (n=18), gemfibrozil (n=10), quinolone antibiotics (n=124), Bactrim® (n=450), and various calcium-channel blockers (dihydropyridines, n=267, diltiazem, n=22 and verapamil, n=5).

Inducers of CYP3A4 (e.g. rifampin, carbamazepine, phenytoin, and barbiturates) have been shown or have the potential to decrease exposure to Everolimus. If these drugs are necessary, Everolimus doses may have to be increased. Potent inhibitors of

CYP3A4 such as ketoconazole, itraconazole and fluconazole should be avoided while the patient is on study medication. Everolimus has the potential to increase the exposure to terfenadine, astemizole and cisapride; hence these drugs should be avoided. In vitro data suggested that Everolimus may have the potential to interact with quinidine, fluoxetine and paroxetine, and alternative medications should be considered. Since the potential for drug interaction with digoxin has not been evaluated, patients on digoxin should have periodic measurement of digoxin levels.

